9.1 Urine Sample Collection for Biomarker Analysis

A urine sample will be collected at Visits 2 through 7. Urine will be collected upon arrival at the study site. Participants will be instructed to not void their bladders for approximately 2 hours before the study visit. The total volumes for each urine void will be recorded.

9.2 Blood Sample Collection for Biomarker Analysis

Blood sample collections for analytical labs will be collected at Visits 2 through 7. Blood samples should be collected after urine collection following vital sign measurements. Subject visits should be scheduled such that blood samples can be collected as late in the day as possible and preferably at the same or similar time with each visit.

9.3 Exhaled CO Measurement

Exhaled CO measurement tests should occur immediately after blood collection. A standard exhaled CO Test will be performed with Micro+™ Smokerlyzer® CO monitors (or equivalent) following the manufacturer's instructions.

10. DEFINITION OF ANALYSIS POPULATIONS

Safety population includes subjects who have tried the test product during the study, including those subjects who participated only in the screening phase.

Intent to treat (ITT) population includes every subject who is randomized according to the randomization schedule.

Modified Intent to Treat (mITT) population includes every subject who has completed the baseline visit and has at least one post-baseline outcome measures.

Per-protocol population is defined as a subset of the ITT population, which is comprised of subjects who completed the study without any major protocol violations.

All protocol deviations that occur during the study will be considered for their severity and impact and will be taken into consideration when subjects are assigned to analysis populations. Details of subject assignment to the analysis populations will be listed.

11. STATISTICAL METHODOLOGY

11.1 General

Data listings will be provided for all subjects up to the point of withdrawal, with any subjects excluded from the relevant population highlighted. Summary statistics and statistical analyses will generally only be performed for subjects included in the relevant analysis population. For the calculation of summary statistics and statistical analysis, unrounded data will be used. For continuous data, summary statistics will include the number of non-missing values (N), mean, median, standard deviation (SD), minimum (min), maximum (max). For categorical data, frequency counts and percentages will be presented.

Mean change from baseline is the mean of all individual subjects' change from baseline values. Each individual change from baseline will be calculated by subtracting the individual subject's baseline value from the value at the timepoint. The individual subject's change from baseline values will be used to calculate the mean change from baseline using a SAS® procedure such as Proc Univariate.

Mean percent change from baseline is the mean of all individual subjects' percent change from baseline values. Each percent change from baseline will be calculated by subtracting the individual subject's baseline value from the value at the desired timepoint and then dividing this calculated value by the individual subject's baseline value and multiplying by 100. These

individual subjects' percent changes from baseline values will be used to calculate the mean percent change from baseline using a SAS® procedure such as Proc Univariate.

Missing values will not be imputed.

Data analysis will be performed using SAS® Version 9.1.3 or higher.

11.2 Definition of Baseline for Calculating Change

The Baseline Period is from Day 1 to Day 8. The baseline for calculating change from baseline will be defined in the following table.

Metric	Baseline	Corresponding post-baseline visits
Quit Attempts and Quitting Intentions	Day 1 (Visit 2)	Day 36 (Visit 7)
Fagerstrom Test for Cigarette Dependence (FTCD)	Day 8 (Visit 3)	Day 36 (Visit 7)
BOE	Day 8 (Visit 3)	Visits 4, 5, 6, 7
CPD daily tracking from IVRS	The average of available data from Day 2 through Day 8	Daily CPD Day 9 to 36 or the average of last week at Visits 4, 5, 6, 7
Vital Signs	Day 8, including unscheduled (rechecked) values	Visits 4, 5, 6, 7
*see Section 11.4.3 for more details		

Rationale for the baseline choices for calculating change:

Quit attempts and intentions: Day 1 is the only one measurement in baseline.

FTCD: There are 2 measurements in the baseline, Day 1 and 8. Day 8 is selected because it is anticipated that there will be changes in CPD, a key component of the FTCD score, when adult smokers are asked to track their daily cigarette consumption. Day 1 value does not reflect this change.

BOE: Day 8 is the last of the 2 baseline values and is closer to the post-baseline values.

CPD daily tracking: The weekly average was selected to adjust for the daily variability and also because total NNAL (primary end-point) has a longer half-life and the average CPD might be better representative of changes in exposure to total NNAL than the individual values.

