6. STUDY DESIGN

This is a randomized, controlled, open-label, parallel group, multi-center, 5-week pilot study to determine changes in BOE in adult smokers allowed *ad libitum* use of VBM-FG2 relative to adult smokers who are not allowed use of VBM-FG2. The data collected from this study will be used to estimate the variability of differences in the percent change from Baseline to the EOS in urinary total NNAL between Test and Control Groups; these findings will be used to estimate the sample size for a future pivotal study. This study will be conducted in approximately 150 adult

smokers who are considered to be in overall good health. Subjects will be randomized (based on gender, daily cigarette consumption [<20 and 20], and quit attempts [any quit attempts/no quit attempts]) to Test (allowed VBM-FG2 use) or Control (not allowed VBM-FG2 use) product in a 3:2 ratio (90 subjects randomized to Test: 60 subjects randomized to Control) with no more than a 60:40 distribution of either males or females to either group.

Screening	Baseline Period*		Product Use Period ^t			
Visit 1	Visit 2	Visit 3	Visit 4	Visit 5	Visit 6	Visit 7
Day -28 to Day -1	Day 1	Day 8±1	Day 15 ± 1	Day 22 ± 1	Day 29± 1	Day 36 ± 1
Subject evaluated against inclusion and exclusion criteria for study eligibility	Baseline CPD data gathered using recall of previous week and daily IVRS call.		Randomization in a 3:2 ratio (Test:Control) 
 • Test = ad libitum VBM-FG2 • Control = no VBM-FG2 			
Enrollment		Randomization				

*Baseline Period = after the daily IVRS call on Day 1 through the daily IVRS call on Day 8.

^t Product Use Period = after the daily IVRS call on Day 8 through the daily IVRS call on Day 36.

Note: Subjects in both groups are allowed to smoke their regular brand cigarettes during the entire study period

Expected duration of the study, from first subject first visit through last subject last visit is approximately 3 months. Expected duration for each subject is expected to be up to approximately 5 weeks (potentially 9 weeks from Screening to EOS). All subjects will be informed that they are allowed to smoke their own cigarettes or to quit smoking during the study.

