Screening (Visit 1) will occur within 28 days of Day 1 (Day -28 to Day -1). An informed Consent Form (ICF) must be signed prior to conducting any study related procedures. Potential subjects will undergo an initial evaluation (vital signs, urine pregnancy test [females only], and questionnaires) to determine initial eligibility. If the subject passes the initial evaluation, then he/she will be provided with a sample of VBM-FG2 and asked to use the product as they like for 15 minutes. Subjects will then complete a Potential Purchase Interest Questionnaire. If they indicate that they "definitely would buy" or "probably would buy" the product on the questionnaire, then the subject will undergo the rest of the screening procedures (clinical labs and electrocardiogram [ECG]). Laboratory values will be evaluated by a local laboratory.

Subjects will return to the study site on the evening of Day 1 for Visit 2. A physical examination will be conducted and subjects who satisfy all the inclusion criteria and exclusion criteria will be eligible for enrollment in the study. Once a subject is enrolled in the study (Day 1), if they choose to no longer participate, they will be considered a drop-out/early termination subject.

During the Baseline Period, at Visits 2 and 3 (Days 1 and 8), blood and urine samples will be collected for analysis of BOE. Subjects will also complete the Past 7 Day Cigarettes Use Questionnaire while at the study site, to indicate their CPD over the previous week. During the Baseline Period (Days 1 to 8) subjects will report CPD daily through an IVRS.

At Visit 3, approximately 150 subjects will be randomized to either the Test or Control Group in a 3:2 ratio (with not more than a 60:40 distribution of either males or females to either group). VBM-FG2 will be dispensed to subjects randomized to the Test Group for *ad libitum* use beginning after the Day 8 IVRS.

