11.4.1 Statistical Analyses of Primary Endpoint

A linear mixed model for repeated measures analysis of variance will be used for the analysis of the primary outcome measure. SAS procedure Proc Mixed will be used for the statistical computing. The null hypothesis is that smokers allowed *ad libitum* use of VBM-FG2 discs (test) will not differ in the primary biomarker (percent change from baseline to EOS in urinary total

NNAL) compared to smokers not allowed use of VBM-FG2 discs (control). The alternative hypothesis is that smokers allowed *ad libitum* use of VBM-FG2 discs will differ in the primary biomarker compared to smokers not allowed use of VBM-FG2 discs. The model will include percent (or absolute) change from baseline to EOS in urinary total NNAL as a response variable, product, visit, and product by visit interaction as fixed effects; and subject as random effect. In the expanded model, several additional factors will be considered. Details about the models are as follows:

Model 1:

Percent (or absolute) change from baseline in total NNAL = study group + visit + study group*visit + subject + random error

Model 2:

Percent (or absolute) change from baseline in total NNAL = study group + visit + study group*visit + subject + CPD + sex + race + body mass index (BMI) + age + random error

where

CPD = fixed covariate representing average number of cigarettes per day for past week from IVRS

study group = fixed effect term (test or control)

sex = fixed effect (male or female)

race = fixed effect (White or Non-White)

BMI = fixed effect covariate

age = fixed effect covariate (continuous)

visit = fixed effect term representing days (ordinal categorical variable)

subject = random subject effect

baseline = Total NNAL measure at Day 8

If the study group*visit interaction term is not statistically significant (P-value > 0.10), then the interaction term will be removed from the model and all comparisons will be done using the overall product means. If the interaction effect is significant (P-value < 0.10), then the comparisons will be conducted for each study visit. Comparisons between products will be done based on 5% level of significance.

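### The primary NNAL models omit a baseline NNAL covariate although Day 1 and Day 8 values are both collected before randomised product, which costs precision without causing bias.

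*SAP*

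**What the plan says.** - **Sampling.** Section 6: "During the Baseline Period, at Visits 2 and 3 (Days 1 and 8), blood and urine samples will be collected for analysis of BOE". Randomisation follows: "At Visit 3, approximately 150 subjects will be randomized to either the Test or Control Group in a 3:2 ratio". Product is dispensed for use after the Day 8 IVRS call. The only earlier contact with the product is at Screening, where each candidate who passes the initial evaluation is given a short trial ("he/she will be provided with a sample of VBM-FG2 and asked to use the product as they like for 15 minutes"). It precedes both samples and applies to both arms.
- **Baseline.** Section 11.2 uses Day 8 for all biomarkers, with the reason "BOE: Day 8 is the last of the 2 baseline values and is closer to the post-baseline values". Section 11.4.1 repeats this for the primary endpoint: "baseline = Total NNAL measure at Day 8".
- **Models.** In section 11.4.1, Model 1 has study group, visit, their interaction and a random subject effect. Model 2 adds CPD, sex, race, BMI and age. Neither has a baseline NNAL term. Section 11.4.2 follows the same pattern for the other biomarkers.
- **Use of Day 1 NNAL.** It appears in a secondary paired t test against Day 8 and in regressions on cigarette counts, both in section 11.4.2. It does not enter the primary analysis.
- **Purpose.** Sections 6 and 8 say that the pilot is to estimate the variability of the primary outcome for a pivotal sample size. No SD, correlation, effect size or power is stated.

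**The concern.** A change score carries the error of its baseline value. A Day 8 spot-urine value that happens to be low makes every later percent change for that subject look high, and the reverse. A baseline covariate lets the model recognise part of that error. A second baseline value helps it more, because it shows whether the Day 8 value was unusual for the subject. Both values will be in the database, but the models use neither in this way.

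Two things are at stake: the precision of the Test-Control comparison, and the usefulness of the pilot for planning. As written, the sponsor would learn the variability of percent change without adjustment. It would not learn how far baseline adjustment, or a second baseline sample, could lower the residual SD in the pivotal trial.

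**Working it through.** The SAP states no SD or power, so there is no figure of its own to reproduce beyond the allocation: 150 × 3/5 = 90 and 150 × 2/5 = 60, which agrees with "90 subjects randomized to Test: 60 subjects randomized to Control".

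**Inputs from the SAP.** 90 Test and 60 Control; two-sided test ("Comparisons between products will be done based on 5% level of significance", with an alternative that the groups differ); percent change from Day 8 as response.

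**Inputs assumed.** Between-subject SD of log NNAL 0.8; within-subject log SD 0.3, 0.4 or 0.5; independent errors; a true 20% reduction; no variation in response between subjects; one post-baseline value (Day 36).

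**Step 1: algebra on the log scale.** Let ρ be the correlation between two values from the same subject, ρ = 0.64/(0.64 + within-subject variance). In units of the total variance, the residual variance of the change is:
- no covariate: 2(1 − ρ)
- Day 8: 1 − ρ²
- Day 8 and Day 1: 1 − 2ρ²/(1 + ρ)

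The ratios are therefore (1 + ρ)/2 for Day 8 against none, (1 + 2ρ)/[2(1 + ρ)] for both against none, and (1 + 2ρ)/(1 + ρ)² for both against Day 8.

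| Within SD | ρ | Day 8 / none | Both / none | Both / Day 8 |
|---|---|---|---|---|
| 0.3 | 0.64/0.73 = 0.877 | 0.94 | 0.73 | 0.78 |
| 0.4 | 0.64/0.80 = 0.800 | 0.90 | 0.72 | 0.80 |
| 0.5 | 0.64/0.89 = 0.719 | 0.86 | 0.71 | 0.83 |

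Day 1 on its own adds nothing under these assumptions. The log change is the Day 36 error minus the Day 8 error plus the treatment effect, and Day 1 is uncorrelated with both errors. It helps only once Day 8 is also in the model.

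**Step 2: percent-change scale.** The SAP's response is percent change, so 3,000 trials of 90 against 60 were simulated with log Day 8 and log Day 1 NNAL as covariates.

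| Within SD | Residual SD, none | Residual SD, both | Variance cut vs none | Variance cut vs Day 8 alone | Power, none to both |
|---|---|---|---|---|---|
| 0.3 | 42.7 | 37.2 | 1 − (37.2/42.7)² = 24% | 20% | 0.85 to 0.92 |
| 0.4 | 63.4 | 55.5 | 1 − (55.5/63.4)² = 23% | 16% | 0.59 to 0.70 |
| 0.5 | 90.3 | 79.3 | 1 − (79.3/90.3)² = 23% | 13% | 0.40 to 0.49 |

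Type I error stayed at 0.046-0.050. Separate simulations under the same assumptions agree to within rounding; across them the variance cut is about 22-25% and the power gain about 6-11 points. Both of these ranges compare both covariates with none, so they include the contribution of Day 8. The residual SD with Day 8 alone follows from the table: 37.2/√0.80 = 41.6, 55.5/√0.84 = 60.6 and 79.3/√0.87 = 85.0.

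**Step 3: less favourable assumptions.** Within SD 0.4, both covariates against none:
- response varying between subjects (log SD 0.3): SD 76.8 to 69.8
- subject-specific Day 1 shift (log SD 0.4): 63.2 to 57.3
- within-subject weekly AR(1) 0.5: 60.3 to 55.7
- within-subject weekly AR(1) 0.8: 44.2 to 42.6

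Day 1 beyond Day 8 alone:
- AR(1) 0.8, within SD 0.3 to 0.4: about 2% in variance. In one such run the SD went from 30.7 to 30.4, (30.4/30.7)² = 0.98, and power from 0.979 to 0.981.
- Widely varying response (log SD 0.6): 5-6% in variance and about 0.01 in power.

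**The case against.** The strongest reply is that the SAP makes a reasoned, pre-specified choice. Day 8 is the last value before product, and the SAP treats Days 1 and 8 as different conditions. Section 11.2 expects daily tracking to change smoking (said of the FTCD), and the Day 1 to Day 8 difference in every biomarker is a secondary endpoint. A pilot without a power target also breaches no stated aim by losing power.

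Much of this stands. Day 8 is a sound baseline and should remain. It does not answer the point about covariates: both samples precede randomisation, so a shift common to the arms cannot bias the comparison, and the regression gives little weight to a Day 1 value that predicts poorly. A plain average of the two days would lack that protection.

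Two stronger readings are tempting, and the document supports neither.
- A reader might infer that the single Day 8 value inflates the SD the pilot is meant to supply. Adding covariates leaves the SD of percent change as it is and lowers only the adjusted residual SD. The unadjusted SD is the right planning figure if the pivotal trial uses one baseline value and the same model.
- A reader might infer from the remark that "total NNAL (primary end-point) has a longer half-life" that Days 1 and 8 measure nearly the same level. That remark explains why CPD is averaged over the week and gives no figure. Strong persistence would also make Day 1 largely redundant.

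The objection on missing data stands too. Section 11.1 rules out imputation, and section 9 sets a urinary biomarker to missing when creatinine is missing or out of range. A required Day 1 covariate without a rule would drop subjects who have valid Day 8 and Day 36 values.

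**Conclusion.** The point holds as a loss of precision that is nearly free to avoid. It is not a bias, a contradiction or a fault in choosing Day 8. Under the independent-error assumptions above, the two covariates together lower residual variance by roughly a quarter. Much of that comes from Day 1, but only with Day 8 beside it. The direction is secure and the size is not, because the SAP gives no within-subject SD or correlation. In the less favourable cases the gain from Day 1 nearly vanishes, and none of the cases tried showed a loss. The calculation uses one post-baseline value and leaves out the Model 2 covariates, so it indicates the scale of the gain and does not forecast it for the full repeated-measures model.

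**What to change.** - Keep Day 8 as the baseline for calculating change, so the endpoint is unchanged.
- In section 11.4.1, add log Day 8 and log Day 1 total NNAL together as covariates in Models 1 and 2. Do the same for the other biomarkers in section 11.4.2.
- State a rule for a missing Day 1 value: fill the covariate from Day 8, or use a missing-value indicator, so that no subject is lost. Note it as an exception to the no-imputation statement in section 11.1, confined to this covariate.
- For pivotal planning, report three figures: the unadjusted SD of percent change, the residual SD with Day 8 alone, and the residual SD with both days. The sponsor can then judge whether a second baseline sample is worth taking.
- List the change in section 13 if the protocol specifies the models without these terms.

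The cost is model wording, one or two degrees of freedom and the missing-covariate rule. No new data are needed.

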11.3 Criteria for Evaluation

11.3.1 Primary Endpoint

The primary outcome measure or endpoint is differences in the percent change from Baseline to the EOS in urinary total NNAL between Test and Control Groups.

11.3.2 Secondary Endpoints

The secondary outcome measures or endpoints are:

- Differences in all BOE during the Baseline Period between Day 1 (weekly recall) versus Day 8 (daily tracking using IVRS).
- Difference in CPD during the Baseline Period between once weekly recall (Days 1 and 8) versus daily tracking (average of recordings on Days 2 through 8).
- Differences in the percent change from Baseline to EOS in BOE (urinary NE, S-PMA, blood COHb, exhaled CO) and CPD between the Test and Control Groups.
- Differences from Baseline to EOS in all BOE and CPD between the Test and Control Groups.
- Proporation of subjects in subgroups based on cigarette consumption change from Baseline to EOS (no change, <50% reduction, 50% reduction, 100% reduction, increase) within and between the Test and Control Groups.
- Proporation of subjects in subgroups based on total NNAL change from Baseline to EOS (no change, reduction, increase) within each group.
- Changes from Baseline (Day 8) to EOS in total scores of Fagerstrom Test for Cigarette Dependence (see Appendix 1), within and between the Test and Control Groups.
- Changes from Baseline (Day 1) to EOS on the Quit Attempts and Quitting Intentions, within and between the Test and Control Groups.

11.3.3 Safety Endpoints

Safety analyses will be conducted on the safety population. Safety analyses will include summaries of AEs as well as summaries of vital signs and laboratory test results.

11.4 Statistical Analyses of Endpoints

All descriptive and inferential statistical analyses will be performed using SAS software.

11.4.1 Statistical Analyses of Primary Endpoint

A linear mixed model for repeated measures analysis of variance will be used for the analysis of the primary outcome measure. SAS procedure Proc Mixed will be used for the statistical computing. The null hypothesis is that smokers allowed *ad libitum* use of VBM-FG2 discs (test) will not differ in the primary biomarker (percent change from baseline to EOS in urinary total

NNAL) compared to smokers not allowed use of VBM-FG2 discs (control). The alternative hypothesis is that smokers allowed *ad libitum* use of VBM-FG2 discs will differ in the primary biomarker compared to smokers not allowed use of VBM-FG2 discs. The model will include percent (or absolute) change from baseline to EOS in urinary total NNAL as a response variable, product, visit, and product by visit interaction as fixed effects; and subject as random effect. In the expanded model, several additional factors will be considered. Details about the models are as follows:

Model 1:

Percent (or absolute) change from baseline in total NNAL = study group + visit + study group*visit + subject + random error

Model 2:

Percent (or absolute) change from baseline in total NNAL = study group + visit + study group*visit + subject + CPD + sex + race + body mass index (BMI) + age + random error

where

CPD = fixed covariate representing average number of cigarettes per day for past week from IVRS

study group = fixed effect term (test or control)

sex = fixed effect (male or female)

race = fixed effect (White or Non-White)

BMI = fixed effect covariate

age = fixed effect covariate (continuous)

visit = fixed effect term representing days (ordinal categorical variable)

subject = random subject effect

baseline = Total NNAL measure at Day 8

If the study group*visit interaction term is not statistically significant (P-value > 0.10), then the interaction term will be removed from the model and all comparisons will be done using the overall product means. If the interaction effect is significant (P-value < 0.10), then the comparisons will be conducted for each study visit. Comparisons between products will be done based on 5% level of significance.

Least squares mean and standard error for the product effect will be estimated by study group and visit with P-values. P-values will also be provided for other effects in Model 2. While group comparison will be made on multiple visits in the model, the difference in change from baseline to the last visit will be the primary comparison and other comparisons will be secondary.

The models will be applied on both the mITT and the Per-protocol populations.

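### The primary model assumes one variance at all four post-baseline visits, so the standard error and P-value of the last-visit comparison are wrong in either direction if the variance differs by visit

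*SAP*

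**What the plan says.** SAP section 11.4.1 describes the primary model in words, with "product, visit, and product by visit interaction as fixed effects; and subject as random effect", and again as an equation: "Percent (or absolute) change from baseline in total NNAL = study group + visit + study group*visit + subject + random error". Model 2 adds covariates and leaves the random part unchanged. The section calls this a repeated-measures mixed model fitted in Proc Mixed. It names no covariance structure across visits, no fallback and no degrees-of-freedom method.

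On the estimand, the section states that "the difference in change from baseline to the last visit will be the primary comparison and other comparisons will be secondary". It also has an interaction rule: if the group-by-visit P-value exceeds 0.10, the interaction is removed and groups are compared on overall means.

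Section 6 says of the pilot's variability findings that "these findings will be used to estimate the sample size for a future pivotal study". Section 11.1 plans an ordinary SD for every continuous variable. Section 12 plans an SD by study group for the primary endpoint variable at the interim analysis, which is meant to inform the pivotal study. No section says which SD will be used for pivotal sizing.

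**The concern.** A random subject intercept plus independent error is compound symmetry: every visit has the same variance and every pair of visits the same correlation. That is a strong assumption for a change from Day 8 measured at four successive weeks, when product use is ad libitum and subjects may go on smoking or quit. The spread of individual changes may well differ between Day 15 and Day 36.

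If it does, the model averages the four visit variances and applies the average to Day 36. The estimated last-visit difference is the same with complete data, but its standard error, and so the primary P-value, is wrong. It is too small if Day 36 is more variable than the average visit, and too large if it is less variable.

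**Working it through.** **Inputs from the SAP.** Four post-baseline visits (section 11.2); 90 Test and 60 Control (section 6); "Comparisons between products will be done based on 5% level of significance" (section 11.4.1). The test is two-sided, because the alternative is that smokers with ad libitum "use of VBM-FG2 discs will differ in the primary biomarker compared to smokers not allowed use of VBM-FG2 discs". The SAP states no SD, effect size or power, so there is no figure of its own to reproduce.

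**Assumed.** Visit SDs in percentage points, the same in both groups, and complete data.

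**Formulas.**
- Group factor: sqrt(1/90 + 1/60) = sqrt(5/180) = 1/6.
- SD carried by the model at every visit: pooled SD = sqrt(mean of the four visit variances).
- Model standard error at the last visit = pooled SD / 6. Correct standard error = SD at Day 36 / 6.
- Actual type I error = 2 × [1 − Φ(1.96 × pooled SD / SD at Day 36)].

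**Example, 30/35/40/45.** Mean variance = (900 + 1225 + 1600 + 2025)/4 = 1437.5, so the pooled SD is 37.9. Model standard error = 37.9/6 = 6.32; correct = 45/6 = 7.50. Ratio 0.843; 1.96 × 0.843 = 1.65; type I error 9.9%.

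| Assumed SDs, Days 15/22/29/36 | Pooled SD | Model SE | Correct SE | Actual type I error |
|---|---|---|---|---|
| 40/40/40/40 | 40.0 | 6.67 | 6.67 | 5.0% |
| 36/39/42/45 | 40.6 | 6.77 | 7.50 | 7.7% |
| 30/35/40/45 | 37.9 | 6.32 | 7.50 | 9.9% |
| 45/40/35/30 | 37.9 | 6.32 | 5.00 | 1.3% |

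**Check by simulation.** With 20,000 simulated trials per pattern and constant or decaying correlation between visits, last-visit rejection rates fell within about half a percentage point of the table. The correlation pattern makes little difference: with complete data and a full group-by-visit model, the last-visit standard error depends only on the visit variances.

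**Effect of the interaction rule.** When the interaction is dropped and overall means are compared, the test rejected at 4.7% to 5.5% in every pattern. Following the whole rule (last visit if the interaction P-value is below 0.10, overall mean otherwise) gave about 7% for 36/39/42/45 and about 8% for 30/35/40/45. With equal SDs it was already nearly 6%, so part of that excess comes from the interaction rule and not from the covariance.

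**Pivotal sizing, only if the model's SD were used.** Sample size scales with the variance, so the ratio of calculated to required n is (pooled SD / SD at Day 36)². This is 1651.5/2025 = 0.82 (18% too small) for 36/39/42/45, 1437.5/2025 = 0.71 (29% too small) for 30/35/40/45, and 1437.5/900 = 1.60 (60% too large) for 45/40/35/30. The raw descriptive SD at Day 36 is not distorted: in simulation it averaged 44.9 for a true 45 and 30.0 for a true 30.

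**The case against.** **The SAP under-specifies but does not forbid.** Proc Mixed and the repeated-measures label leave room for a visit-level covariance. That is fair as far as it goes, but the model is written out twice with subject and random error only. A programmer following the equation would fit a random intercept. If another structure is allowed, the primary P-value is not uniquely prespecified, and the same sentence is needed.

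**The main deliverable is safe.** A reader might infer that the pilot's variability estimate will be understated and the pivotal study undersized. The documents do not support this. Section 11.4.1 takes least squares means, standard errors and P-values from the model, not an SD. Sections 11.1 and 12 plan descriptive SDs that do not depend on it. This objection stands; what remains is that the SAP does not say which SD will be used.

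**Variance need not grow.** A reader might take the remark in section 11.2 that "total NNAL (primary end-point) has a longer half-life" as evidence that subjects diverge over time and the standard error is therefore too small. That remark justifies averaging cigarettes per day over a week and says nothing about variance by visit. Rising variance is plausible but not shown, and falling variance makes the test conservative. This stands too.

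**The interaction rule blunts the effect.** When overall means are compared, the fault disappears. That is correct, and the type I figures belong to the last-visit contrast. But that contrast is the one section 11.4.1 calls primary.

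**Conclusion.** The point holds in limited form. As written, the primary model assumes a common variance at Days 15, 22, 29 and 36, while the primary comparison concerns Day 36 alone. If the variances differ, the last-visit standard error and P-value are wrong, and the SAP provides no protection.

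The illustrated type I error runs from 1.3% to 9.9% around a nominal 5%, and is exactly 5% if the variances are equal. These figures rest on assumed visit SDs, equal SDs in the two groups, complete data, 90/60 subjects and the last-visit contrast. The SAP supplies no data to say which pattern is likely. For the pivotal planning SD, the finding is only that its source is not named.

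**What to change.** In section 11.4.1, replace the random subject intercept with an unstructured covariance over the four post-baseline visits (repeated visit within subject), with Kenward-Roger degrees of freedom. Name heterogeneous Toeplitz as the fallback if the model does not converge. The last-visit standard error then rests on the Day 36 variance, whether variances are equal, rising or falling.

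In section 6 or 8, state that the descriptive Day 36 SD of percent change in total NNAL, by study group, is the planning figure for the pivotal study. The descriptive SD is the right source here, because a single unstructured matrix yields one Day 36 SD pooled over the groups, not one per group.

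Cost: a line or two of SAP text and a line of code. The downside is 10 covariance parameters instead of 2, which about 150 subjects can support.
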